3.1 Administration Schedule

All patients will receive trametinib 2mg daily continuously until intolerable toxicity, disease progression, or the end of the study.

Trametinib should be administered once per day, continuously; and should be taken at about the same time each day. The study drug should be administered together with approximately eight ounces of water. Trametinib should be taken fasting, at least 1 hour before or 2 hours after a meal. If a subject vomits after taking study medication, the subject should be instructed not to retake the dose and should take the next scheduled dose.

If a dose of trametinib is missed, only take the dose if it is more than 12 hours until the next scheduled dose.

Trametinib should be stored at 2-8°C (36-46°F). Refrigerate. Do not freeze.

3.2 Adverse Event Reporting Requirements

The Adverse Event Reporting Requirements for all EAY131 subprotocols are outlined in the MATCH MASTER protocol. Please refer to those guidelines when determining if an event qualifies as a Serious Adverse Event (SAE) and requires expedited reporting via CTEP's Adverse Event Reporting System (CTEP-AERS).

In addition, the following section outlines agent specific requirements and must be followed to ensure all reporting requirements are met.

3.2.1 Additional instructions, requirements and exceptions for protocol EAY131-Subprotocol S2.

Additional Instructions

For instructions on how to specifically report events that result in persistent or significant disability/incapacity, congenital anomaly, or birth defect events via CTEP-AERS, please contact the AEMD Help Desk at [contact] or [contact]. This will need to be discussed on a case-by-case basis.

EAY131- Subprotocol S2 specific expedited reporting requirements:

- **LVEF Changes:** If any of the following circumstances occur, the event(s) must be reported via CTEP-AERS according to the timeframes outlined in the AE table in section 5.3.6 of the MATCH Master protocol
 - Asymptomatic: Absolute decrease of >10% in LVEF compared to baseline and ejection fraction below the institution's LLN and LVEF **does not recover** within 4 weeks
 - Symptomatic: Grade 3-4 LVEF

Rev. 5/16

Please refer to the dose modification instructions for further information regarding Treatment Modification and Management Guidelines for LVEF Decrease

- **Visual Changes:** If RPED (retinal pigment epithelial detachments) or RVO (retinal vein occlusion) are diagnosed, the event(s) must be reported via CTEP-AERS according to the timeframes outlined in the AE table in section 5.3.6 of the MATCH Master protocol. Please refer to the dose modification instructions for further information regarding Treatment Modification and Management Guidelines for Visual Changes.
- **Liver Chemistry Changes:** If any of the following circumstances occur, the event(s) must be reported via CTEP-AERS according to the timeframes outlined in the AE table in section 5.3.6 of the MATCH Master protocol
 - ALT \geq 3xULN **and** bilirubin \geq 2x ULN or $>$ 35% direct bilirubin
 - ALT \geq 3xULN **and** INR \geq 1.5, if INR measured (INR threshold does not apply if subject is on anticoagulant)
- Please refer to the dose modification instructions for further information regarding Treatment Modification and Management Guidelines for Liver Chemistry Changes
- **Pregnancies:** Pregnancies and suspected pregnancies (including a positive or inconclusive pregnancy test, regardless of age or disease state) occurring while the female patient is on Trametinib, or within 28 days of the patient subject's last dose of Trametinib, are considered immediately reportable events. The pregnancy, suspected pregnancy, or positive/ inconclusive pregnancy test must be reported via CTEP-AERS within 24 hours of the Investigator's knowledge. Please refer to Appendix VIII in MATCH Master protocol for detailed instructions on how to report the occurrence of a pregnancy as well as the outcome of all pregnancies.

Rev. Add25

EAY131-S2 specific expedited reporting exceptions:

For study Subprotocol S2, the adverse events listed below **do not** require expedited reporting via CTEP-AERS:

- If an AE meets the reporting requirements of the protocol, and it is listed on the SPEER, it should **ONLY be reported via CTEP-AERS if the grade being reported exceeds the grade listed in the parentheses next to the event**

3.2.2 Second Primary Cancer Reporting Requirements

NOTE: The MATCH Master Protocol outlines the standard requirements for the reporting of second primaries. Please be aware that there are additional requirements for this subprotocol. Please adhere to the guidelines outlined below for the reporting of second primaries on this subprotocol.

All cases of second (second malignancy is a cancer that is unrelated to any prior anti-cancer treatment, including the treatment on this protocol) **and** secondary malignancies (secondary malignancy is a cancer caused by any prior anti-cancer treatment, including the treatment on this protocol), including acute myeloid leukemia (AML) and myelodysplastic syndrome (MDS)], regardless of attribution, that occur following treatment on NCI-sponsored trials must be reported as follows:

1. Complete a Second Primary Form in Medidata Rave within 14 days.
2. Report the diagnosis via CTEP-AERS, regardless of attribution, at <http://ctep.cancer.gov>
Report under a.) *leukemia secondary to oncology chemotherapy*, b.) *myelodysplastic syndrome*, or c.) *treatment related secondary malignancy*
3. Upload a copy of the pathology report to ECOG-ACRIN via Medidata Rave and submit a copy to NCI/CTEP confirming the diagnosis.
4. If the patient has been diagnosed with AML/MDS, upload a copy of the cytogenetics report (if available) to ECOG-ACRIN via Medidata Rave and submit a copy to NCI/CTEP.

NOTE: All new malignant tumors must be reported through CTEP-AERS whether or not they are thought to be related to either previous or current treatment. All new malignancies should be reported including solid tumors (including non-melanoma skin malignancies), hematologic malignancies, Myelodysplastic Syndrome (MDS)/Acute Myelogenous Leukemia (AML), and *in situ* tumors.

Whenever possible, the CTEP-AERS report should include the following:

- tumor pathology
- history of prior tumors
- prior treatment/current treatment including duration
- any associated risk factors or evidence regarding how long the tumor may have been present
- when and how the tumor was detected
- molecular characterization or cytogenetics or the original tumor (if available) and of any new tumor
- tumor treatment and outcome (if available)

NOTE: The Second Primary Form and the CTEP-AERS report should not be used to report recurrence or development of metastatic disease.

NOTE: If a patient has been enrolled in more than one NCI-sponsored study, the Second Primary Form must be submitted for the most recent trial. ECOG-ACRIN must be provided with a copy of the form and the associated

pathology report and cytogenetics report (if available) even if ECOG-ACRIN was not the patient's most recent trial.

NOTE: Once data regarding survival and remission status are no longer required by the protocol, no follow-up data should be submitted via CTEP-AERS or by the Second Primary Form.

Rev. 1/17
Rev. Add19
Rev. Add25

3.3 Comprehensive Adverse Events and Potential Risks List (CAEPR) for Trametinib dimethyl sulfoxide (GSK1120212B, NSC 763093)

The Comprehensive Adverse Events and Potential Risks list (CAEPR) provides a single list of reported and/or potential adverse events (AE) associated with an agent using a uniform presentation of events by body system. In addition to the comprehensive list, a subset, the Specific Protocol Exceptions to Expedited Reporting (SPEER), appears in a separate column and is identified with bold and italicized text. This subset of AEs (SPEER) is a list of events that are protocol specific exceptions to expedited reporting to NCI (except as noted below). Refer to the 'CTEP, NCI Guidelines: Adverse Event Reporting Requirements' http://ctep.cancer.gov/protocolDevelopment/electronic_applications/docs/ae guideline.pdf for further clarification. *Frequency is provided based on 1111 patients.* Below is the CAEPR for Trametinib dimethyl sulfoxide (GSK1120212B).

NOTE: If an AE meets the reporting requirements of the protocol, and it is listed on the SPEER, it should **ONLY** be reported via CTEP-AERS if the grade being reported exceeds the grade listed in the parentheses next to the event.

Version 2.6, October 10, 2019¹

Adverse Events with Possible Relationship to Trametinib (GSK1120212B) (CTCAE 5.0 Term) [n= 1111]			Specific Protocol Exceptions to Expedited Reporting (SPEER)
Likely (>20%)	Less Likely (<=20%)	Rare but Serious (<3%)	
BLOOD AND LYMPHATIC SYSTEM DISORDERS			
	Anemia		Anemia (Gr 3)
CARDIAC DISORDERS			
		Heart failure	
		Left ventricular systolic dysfunction	
	Sinus bradycardia		
EYE DISORDERS			
	Blurred vision		
	Dry eye		
		Eye disorders - Other (chorioretinopathy also known as retinal pigment epithelial detachment)	
		Eye disorders - Other (retinal vein occlusion)	
	Eye disorders - Other (visual disorders) ²		
		Papilledema	
	Periorbital edema		
GASTROINTESTINAL DISORDERS			
	Abdominal pain		Abdominal pain (Gr 2)
		Colitis	
		Colonic perforation	
	Constipation		Constipation (Gr 2)

Adverse Events with Possible Relationship to Trametinib (GSK1120212B) (CTCAE 5.0 Term) [n= 1111]			Specific Protocol Exceptions to Expedited Reporting (SPEER)
Likely (>20%)	Less Likely (<=20%)	Rare but Serious (<3%)	
Diarrhea			Diarrhea (Gr 3)
	Dry mouth		Dry mouth (Gr 2)
	Dyspepsia		Dyspepsia (Gr 2)
	Mucositis oral		Mucositis oral (Gr 3)
Nausea			Nausea (Gr 3)
	Vomiting		Vomiting (Gr 3)
GENERAL DISORDERS AND ADMINISTRATION SITE CONDITIONS			
	Chills		Chills (Gr 2)
	Edema face		
Fatigue			Fatigue (Gr 3)
	Fever		Fever (Gr 2)
Generalized edema			Generalized edema³ (Gr 2)
IMMUNE SYSTEM DISORDERS			
	Allergic reaction ⁴		
INFECTIONS AND INFESTATIONS			
	Folliculitis		Folliculitis (Gr 2)
	Lung infection		
	Paronychia		Paronychia (Gr 2)
	Skin infection		Skin infection (Gr 2)
INVESTIGATIONS			
	Alanine aminotransferase increased		Alanine aminotransferase increased (Gr 3)
	Alkaline phosphatase increased		Alkaline phosphatase increased (Gr 2)
	Aspartate aminotransferase increased		Aspartate aminotransferase increased (Gr 3)
	CPK increased		
	Ejection fraction decreased		
METABOLISM AND NUTRITION DISORDERS			
	Anorexia		Anorexia (Gr 3)
	Dehydration		Dehydration (Gr 3)
	Hypoalbuminemia		
	Hypomagnesemia		Hypomagnesemia (Gr 2)
	Hyponatremia		Hyponatremia (Gr 3)
MUSCULOSKELETAL AND CONNECTIVE TISSUE DISORDERS			
	Arthralgia		
	Back pain		Back pain (Gr 2)
	Pain in extremity		Pain in extremity (Gr 2)
		Rhabdomyolysis	
NERVOUS SYSTEM DISORDERS			
	Dizziness		Dizziness (Gr 2)
	Headache		Headache (Gr 2)

Adverse Events with Possible Relationship to Trametinib (GSK1120212B) (CTCAE 5.0 Term) [n= 1111]			Specific Protocol Exceptions to Expedited Reporting (SPEER)
Likely (>20%)	Less Likely (<=20%)	Rare but Serious (<3%)	
RESPIRATORY, THORACIC AND MEDIASTINAL DISORDERS			
	Cough		Cough (Gr 2)
	Dyspnea		Dyspnea (Gr 3)
		Pneumonitis	
SKIN AND SUBCUTANEOUS TISSUE DISORDERS			
	Alopecia		Alopecia (Gr 2)
	Dry skin		Dry skin (Gr 2)
	Nail changes		
		Palmar-plantar erythrodysesthesia syndrome	
	Pruritus		Pruritus (Gr 2)
		Skin and subcutaneous tissue disorders - Other (drug reaction with eosinophilia and systemic symptoms [DRESS])	
Skin and subcutaneous tissue disorders - Other (rash) ⁵			Skin and subcutaneous tissue disorders - Other (rash)⁵ (Gr 3)
		Stevens-Johnson syndrome ⁶	
VASCULAR DISORDERS			
	Hypertension		Hypertension (Gr 3)
		Thromboembolic event (venous)	
	Vascular disorders - Other (hemorrhage) ⁷		

¹This table will be updated as the toxicity profile of the agent is revised. Updates will be distributed to all Principal Investigators at the time of revision. The current version can be obtained by contacting [contact]. Your name, the name of the investigator, the protocol and the agent should be included in the e-mail.

²Visual disorders include visual disturbance that can be associated with conjunctival hemorrhage, corneal graft rejection, cyclitis, eye nevus, halo vision, iritis, macular edema, retinal hemorrhage, visual acuity reduced, visual impairment, and vitreous detachment.

³Generalized edema includes edema, lymphedema, and edema limbs.

⁴Hypersensitivity (allergic reactions) may present with symptoms such as fever, rash, increased liver function tests, and visual disturbances.

⁵Skin and subcutaneous tissue disorders - Other (rash) may include rash, rosacea, rash acneiform, erythematous rash, genital rash, rash macular, exfoliative rash, rash generalized, erythema, rash papular, seborrheic dermatitis, dermatitis psoriasiform, rash follicular, skin fissures, and skin chapped.

⁶Stevens-Johnson syndrome has been observed in patients treated with trametinib and dabrafenib combination.

⁷The majority of hemorrhage events were mild. Major events, defined as symptomatic bleeding in a critical area or organ (e.g., eye, GI hemorrhage, GU hemorrhage, respiratory hemorrhage), and fatal intracranial hemorrhages have been reported.

Adverse events reported on trametinib dimethyl sulfoxide (GSK1120212B) trials, but for which there is insufficient evidence to suggest that there was a reasonable possibility that trametinib dimethyl sulfoxide (GSK1120212B) caused the adverse event:

BLOOD AND LYMPHATIC SYSTEM DISORDERS - Disseminated intravascular coagulation; Febrile neutropenia; Leukocytosis

CARDIAC DISORDERS - Atrial fibrillation; Cardiac arrest; Myocardial infarction; Restrictive cardiomyopathy; Sinus tachycardia

EYE DISORDERS - Corneal ulcer; Eyelid function disorder; Flashing lights; Floaters; Glaucoma; Photophobia

GASTROINTESTINAL DISORDERS - Ascites; Duodenal ulcer; Esophageal necrosis; Esophageal ulcer; Esophagitis; Gastric hemorrhage⁷; Gastric ulcer; Gastritis; Gastrointestinal disorders - Other (intestinal obstruction); Gastrointestinal disorders - Other (pneumatosis intestinalis); Gastrointestinal fistula; Gingival pain; Hemorrhoidal hemorrhage⁷; Ileus; Obstruction gastric; Pancreatitis; Small intestinal obstruction

GENERAL DISORDERS AND ADMINISTRATION SITE CONDITIONS - Flu like symptoms; General disorders and administration site conditions - Other (axillary pain); Localized edema; Malaise; Non-cardiac chest pain; Pain

HEPATOBIILIARY DISORDERS - Cholecystitis; Hepatic failure; Hepatic pain; Hepatobiliary disorders - Other (hepatic encephalopathy)

INFECTIONS AND INFESTATIONS - Biliary tract infection; Catheter related infection; Device related infection; Endocarditis infective; Enterocolitis infectious; Hepatitis viral; Infections and infestations - Other (abscess limb); Infections and infestations - Other (necrotizing fasciitis); Infections and infestations - Other (oral infection); Pharyngitis; Sepsis; Upper respiratory infection; Urinary tract infection

INJURY, POISONING AND PROCEDURAL COMPLICATIONS - Bruising

INVESTIGATIONS - Blood bilirubin increased; Blood lactate dehydrogenase increased; Creatinine increased; Electrocardiogram QT corrected interval prolonged; GGT increased; Lipase increased; Lymphocyte count decreased; Platelet count decreased; Serum amylase increased; White blood cell decreased

METABOLISM AND NUTRITION DISORDERS - Hyperglycemia; Hyperkalemia; Hyperphosphatemia; Hyperuricemia; Hypocalcemia; Hypoglycemia; Hypokalemia

MUSCULOSKELETAL AND CONNECTIVE TISSUE DISORDERS - Generalized muscle weakness; Muscle cramp; Musculoskeletal and connective tissue disorder - Other (compression fracture); Myalgia; Neck pain

NEOPLASMS BENIGN, MALIGNANT AND UNSPECIFIED (INCL CYSTS AND POLYPS) - Tumor hemorrhage⁷; Tumor pain

NERVOUS SYSTEM DISORDERS - Dysgeusia; Encephalopathy; Intracranial hemorrhage⁷; Lethargy; Nervous system disorders - Other (diplopia); Seizure; Somnolence; Stroke; Syncope; Transient ischemic attacks

PSYCHIATRIC DISORDERS - Anxiety; Confusion; Delirium; Depression; Hallucinations; Insomnia; Personality change

RENAL AND URINARY DISORDERS - Acute kidney injury; Cystitis noninfective; Dysuria; Hematuria; Proteinuria; Urinary incontinence

REPRODUCTIVE SYSTEM AND BREAST DISORDERS - Vaginal fistula; Vaginal hemorrhage⁷

RESPIRATORY, THORACIC AND MEDIASTINAL DISORDERS - Bronchopulmonary hemorrhage⁷; Hypoxia; Laryngeal edema; Oropharyngeal pain; Pleural effusion; Pneumothorax; Productive cough; Pulmonary hypertension; Respiratory failure; Sinus disorder

SKIN AND SUBCUTANEOUS TISSUE DISORDERS - Bullous dermatitis; Photosensitivity; Purpura; Skin and subcutaneous tissue disorders - Other (erythema nodosum); Skin ulceration; Urticaria

VASCULAR DISORDERS - Hematoma; Hot flashes; Hypotension

NOTE: Trametinib (GSK1120212B) in combination with other agents could cause an exacerbation of any adverse event currently known to be caused by the other agent, or the combination may result in events never previously associated with either agent.

Rev. 12/16

3.4 Dose Modifications

NOTE: Patients who interrupt trametinib for > 2 weeks will be removed from this subprotocol, unless the interruption was for reduction in LVEF, visual changes or RPED with subsequent recovery as described in corresponding tables below.

All toxicity grades below are described using the NCI Common Terminology Criteria for Adverse Events (CTCAE) version 4.0.

All appropriate treatment areas should have access to a copy of the CTCAE version 4.0. A copy of the CTCAE version 4.0 can be downloaded from the CTEP website (<http://ctep.cancer.gov>).

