3.5.3 Guidelines for Rash

Rash is a frequent AE observed in subjects receiving trametinib (see the Investigator's Brochures [4]) for more information).

Recommendations for supportive care and guidelines for dose modifications for rash are based on experience with other MEK inhibitors and EGFR inhibitors [26, 27] and are provided (see Table 9 and Table 10).

The institutional standards for the management of skin-related AEs can differ from these guidelines. In this case, best clinical judgment should be applied and a consultation with the subprotocol Study Chair may be required.

Table 9 Guidelines for Supportive Care of Rash

Type of Care	Action
Prevention/Prophylaxis ^a	
 • Avoid unnecessary exposure to sunlight • Apply broad-spectrum sunscreen (containing titanium dioxide or zinc oxide) with a skin protection factor (SPF) ≥ 15 at least twice daily. • Use thick, alcohol-free emollient cream (e.g., glycerine and cetomacrogol cream) on dry areas of the body at least twice daily. • Topical steroids and/or antibiotics should be applied at least twice daily starting on Day 1 of study treatment, to body areas such as face, chest, and upper back. Use mild-strength topical steroid (hydrocortisone 1% cream) and/or topical antibiotic (e.g., clindamycin) or oral antibiotics (e.g., doxycycline 100 mg BID, minocycline 100 mg BID)
Symptomatic Care ^b	
 • Pruritic lesions: cool compresses and oral antihistamine therapies • Fissuring lesions: Monsel's solution, silver nitrate, or zinc oxide cream • Desquamation: thick emollients and mild soap • Paronychia: antiseptic bath, local potent corticosteroids in addition to oral antibiotics; if no improvement, consult dermatologist or surgeon • Infected lesions: appropriate bacterial/fungal culture-driven systemic or topical antibiotics

Abbreviations: BID = twice daily; SPF = sun protection factor

- a. Rash prophylaxis is recommended for the first 6 weeks of study treatment
- b. Subjects who develop rash/skin toxicities should be seen by a qualified physician and should receive evaluation for symptomatic/supportive care management

Guidelines for management and dose reduction for rash considered to be related to study treatment are provided (see Table 10).

Table 10 Management and Dose Modification Guidelines for Rash

CTCAE Grade	Adverse Event Management	Action and Dose Modification

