Grade 1	
 Initiate prophylactic and symptomatic treatment measures^a Use moderate strength topical steroid^b Reassess after 2 weeks 	
 Continue study treatment If rash does not recover to baseline within 2 weeks despite best supportive care, reduce trametinib by one dose level^c
Grade 2	
 Initiate prophylactic and symptomatic treatment measures Use moderate strength topical steroid^b Reassess after 2 weeks 	
 Reduce trametinib by one dose level 
 If rash recovers to ≤ grade 1 within 2 weeks, increase dose to previous dose level If no recovery to ≤ grade 1 within 2 weeks, interrupt study treatment until recovery to ≤ grade 1 Restart trametinib at reduced dose level^c
Grade ≥ 3	
 Use moderate strength topical steroids^b PLUS oral methyl-prednisolone dose pack Consult dermatologist 	
 Interrupt trametinib until rash recovers to grade ≤ 1 Restart^c trametinib reduced by one dose level^d If no recovery to grade ≤ 2 within 2 weeks, permanently discontinue trametinib

Abbreviations: CTCAE = Common Terminology Criteria for Adverse Events

- Rash prophylaxis is recommended for the first 6 weeks of study treatment
- Moderate-strength topical steroids: hydrocortisone 2.5% cream or fluticasone propionate 0.5% cream
- Approval of subprotocol Study Chair is required to restart study treatment after > 2 weeks of interruption.
- Escalation of study treatment to previous dose level may be considered if no rash is evident 4 weeks after restarting study treatment

Rev. 12/16

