3.5.5 Trametinib Dose Modification for Toxicities Not Specified in Subsequent Sections

Table 12 Trametinib Treatment Modification for Clinically Significant Toxicities Deemed Related to Trametinib

(This section is not for specific AEs such as hypertension, rash, ejection fraction changes, pneumonitis, diarrhea, liver chemistry, or visual changes. Refer to other sections for these specific AEs).

CTCAE v4 Grade	Management Guideline	Dose Modification
Grade 1	Monitor as clinically indicated. Provide supportive care according to institutional standards.	Continue trametinib at current dose level.
Grade 2 (tolerable)		
 Interrupt treatment until resolution to grade 1 or baseline. Upon resolution, restart treatment at current dose level.
Grade 2 (intolerable) and Grade 3		
 Interrupt treatment until resolution to grade 1 or baseline. Upon resolution to baseline or grade 1, restart with one level of dose reduction. If the Grade 3 toxicity recurs, interrupt trametinib; When toxicity resolves to Grade 1 or baseline, restart trametinib reduced by another dose level.
Grade 4		
If event resolves to grade 1 or baseline discuss potential continuation of trametinib with the subprotocol Study Chair; if continuation of treatment agreed then restart trametinib at dose reduced by one dose level.
 
If event does not resolve, permanently discontinue trametinib.

Trametinib should be discontinued if treatment delay is ≥ 14 days due to toxicities. If the investigator concludes that continued trametinib will benefit a patient, the subprotocol Study Chair may be consulted for the possibility of resuming trametinib, provided that toxicities have resolved to baseline or grade 1.

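### Section 3.4 removes patients after a trametinib hold of more than 2 weeks with three exceptions, yet the rash table provides for restart after such a hold with Study Chair approval

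*Protocol*

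**What the plan says.** The note that opens Section 3.4 sets a general rule: "Patients who interrupt trametinib for > 2 weeks will be removed from this subprotocol, unless the interruption was for reduction in LVEF". The sentence goes on to add visual changes and RPED, in each case with recovery as the relevant table describes. These are the only exceptions, and the note mentions no Study Chair approval.

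Section 3.5.3, Table 10 (rash), deals with the same length of interruption in a footnote: "Approval of subprotocol Study Chair is required to restart study treatment after > 2 weeks of interruption". Two of its rows hold treatment:

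- **Grade 2.** The dose is first reduced by one level. If the rash has not recovered after 2 weeks, the instruction is to "interrupt study treatment until recovery to ≤ grade 1" and then restart at a reduced level. No end date is given for the hold.
- **Grade ≥ 3.** The instruction to hold is "Interrupt trametinib until rash recovers to grade ≤ 1". The instruction to stop for good is "If no recovery to grade ≤ 2 within 2 weeks, permanently discontinue trametinib".

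Section 3.5.5, below Table 12 (toxicities without a table of their own), says: "Trametinib should be discontinued if treatment delay is ≥ 14 days due to toxicities". The next sentence allows the Study Chair to be consulted about resuming if the investigator expects benefit and the toxicity is back to baseline or Grade 1.

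**The concern.** The Section 3.4 note and the Table 10 footnote use the same threshold, more than 2 weeks of interruption, and reach different outcomes. Under the note the patient leaves the subprotocol. Under the footnote the patient may restart if the Chair approves. Both cannot be followed for the same patient.

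The rule decides whether a patient whose toxicity has recovered stays on study drug. With the same rash and the same length of hold, one site could take the patient off while another asks the Chair and restarts. Rash is not a remote case: Section 3.5.3 says "Rash is a frequent AE observed in subjects receiving trametinib".

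**Working it through.** The protocol gives no figure to reproduce here. The check sets the texts side by side and applies each to the same case.

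**Step 1: a hold of 15 days.** Since 15 > 14, the Section 3.4 limit is passed.

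| Reason for hold | Section 3.4 note | Specific section | Same outcome? |
|---|---|---|---|
| Rash | Not an exception: removed | Table 10 footnote: restart possible with Chair approval | No |
| Toxicity covered by Table 12 | Not an exception: removed | 15 ≥ 14: discontinue, but Chair may be consulted on resuming | Same default, but only one text has a way back |

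**Step 2: can Table 10 lead to a hold of more than 2 weeks?** For the Grade ≥ 3 row, take the rash grade 14 days into the hold:

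- Grade 0 or 1: the restart condition (Grade ≤ 1) is met.
- Grade 2: the restart condition is not met. The permanent-stop condition is not met either, because the rash has recovered to Grade ≤ 2. The hold continues past 2 weeks.
- Grade 3 or 4: permanent discontinuation.

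The Grade 2 row holds treatment until Grade ≤ 1 without a time limit, so it too can pass 2 weeks. The Grade 1 row continues treatment and involves no hold. Two of the three rows can therefore produce the situation that the footnote addresses.

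**Step 3: does the footnote belong to these rows?** The footnote letters are not legible in the text available. The Chair-approval note is third of four, which corresponds to marker c, and the restart steps of both rows carry c. The fourth note, on re-escalation, corresponds to marker d on the reduced dose in the Grade ≥ 3 row, which also fits.

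**Step 4: other tables.**

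- Tables 7 (liver chemistry) and 8 (QTc) make restart depend on the Chair's agreement but say nothing on elapsed time. They can operate inside the Section 3.4 limit and are not counted.
- Table 6 (pneumonitis, Grades 2 and 3) and Table 11 (diarrhea, Grade 1 or 2) stop treatment at about two weeks, in line with Section 3.4.
- Section 3.4 and Table 11 act on a delay of more than 2 weeks or 14 days, the Table 12 text on 14 days or more. This is a minor wording difference: stopping at day 14 breaches none of them.

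**Step 5: count.** Section 3.4 names three exceptions. Toxicity groups that are not among them but have an express route to resume beyond the limit: rash (1) + toxicities covered by Table 12 (1) = 2.

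**Step 6: how many patients could be exposed.** The Section 3.3 risk list places rash in its highest frequency column (> 20%). If that frequency held at the accrual goal of 35, then 0.20 × 35 = 7, so more than 7 patients would have rash of any grade. This is an assumption about the pool at risk. The protocol gives nothing from which to derive the share held for more than 2 weeks.

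**The case against.** The strongest reply concerns scope. The note stands at the head of Section 3.4, and its three exceptions correspond to Tables 2, 4 and 5, all within that section. Rash and the remaining toxicities are in Section 3.5, which has its own heading and its own delay rules. If the note applied only to Section 3.4, there would be no conflict. The text does not support that limit: the note speaks of patients who interrupt trametinib without qualification, and its consequence is removal from the whole subprotocol. The two-week limit also recurs in both sections (Table 6 in 3.4, Table 11 in 3.5). Nor does any provision say that a specific table overrides the note; the note handles departures by listing them.

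Other points against carry some weight:

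- The Table 12 text stops treatment by default, as Section 3.4 does, and its route back is discretionary. It is a weaker conflict than rash.
- The row analysis of Table 10 alone would not prove a contradiction, because Section 3.4 could be read as capping an open-ended hold. The footnote's explicit reference to restart after more than 2 weeks closes that reading for rash.
- Marker c also appears in the Grade 1 row, where nothing is interrupted, so the lettering may be imperfect. The footnote's wording does not depend on it.
- Restart after a long hold goes through the Study Chair in both places, so a site cannot restart on its own reading. What can differ is whether the site asks at all.
- The figure of more than 7 patients describes rash of any grade and does not measure the problem.

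**Conclusion.** The concern holds. For rash, Section 3.4 and the Table 10 footnote contradict each other at the same threshold and cannot both be followed. For toxicities under Table 12 the conflict is real but milder. No text says which provision governs.

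The size is two toxicity groups outside a list of three exceptions, with two of the three rash rows able to produce a hold beyond 2 weeks. The conclusion rests on reading the Section 3.4 note as unrestricted, as it is written. It does not rest on the assumed rash frequency. The number of patients affected is unknown and no endpoint effect is claimed. It should be corrected because it is an operative rule on who stays on study drug.

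**What to change.** Reconcile the Section 3.4 note, the Table 10 footnote with its Grade 2 and Grade ≥ 3 rows, and the text under Table 12. After the change they should agree on whether restart is possible after a hold of more than 2 weeks and by whose approval, and the protocol should say which text governs if they differ. The same amendment should state whether the Section 3.4 limit applies to Tables 7 and 8, which are silent on time. The sponsor's clinical team decides the content, including whether limits differ by toxicity. The cost is amendment wording, with no added visits, tests or patients.
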